8.2 Handling of Missing Data

Missing data will be imputed using the following methods for the efficacy analyses:

- Non-Responder Imputation (NRI): the NRI analysis will categorize any subject who does not have evaluation during a specific visit window as a non-responder for that visit. Unless otherwise noted, this will be the primary approach for accounting for missing data in responder analyses.
- Generalized linear mixed model (GLMM): The model will include a logit link function to compare the probability of having responder between treatment groups of each visit of Day 2-4, Week 4, Week 8, Week 12, Week 24, Week 36, Week 52, and will include baseline NIHSS as a covariate and time from last known normal and initiation of first dose (≤ 12 hours, > 12 hours), tPA use (Y/N), EVT use (Y/N), visit, and treatment group as fixed effects. An unstructured variance covariance matrix will be used. The compound symmetry variance covariance matrix will be used if the model does not converge with unstructured matrix. The GLMM model relies on a missing at random (MAR) assumption.
- As Observed (AO): The AO analysis will not impute values for missing evaluations, and thus a subject who does not have an evaluation on a scheduled visit will be excluded from the AO analysis for that visit. AO will include all values collected in the study.
- MMRM: The repeated measures analysis will be conducted using a mixed model including observed measurements at all visits. The mixed model includes the categorical fixed effects of treatment, visit and treatment-by-visit interaction, main stratification factors at randomization, and the continuous fixed covariates of baseline measurement, unless otherwise noted. An unstructured variance-covariance matrix will be used; if the model does not converge, then a compound symmetry variance-covariance matrix will be used. Denominator degrees of freedom will be computed using the Kenward-Roger method. Parameter estimation is based on the assumption of data being missing at random and using the method of restrictive maximum likelihood. MMRM will be the primary approach in the analysis of continuous

variables unless otherwise noted. The MMRM model relies on a missing at random (MAR) assumption.

For all analyses related to the mRS, if a subject has a value of 6 (dead), this will be carried forward to future visits in the analysis. This will be applied to all mRS analyses, including the responder analysis as observed.

The COVID-19 pandemic is interfering with the conduct of many ongoing trials, with potential impact on treatment duration and the collection, analysis and the interpretation of clinical trial data. Some protocol-specified visits in this clinical trial may be impacted due to COVID-19 infection or logistical restrictions during the pandemic. For example, some scheduled visits may be missed due to self-quarantine or local government restrictions on travel; some visits may also be delayed or canceled due to healthcare resource constraints during the pandemic. These missed visits will be recorded in the database. The probability of having missed visits and missing data due to COVID-19 infection or logistical restrictions related to the COVID-19 pandemic can be reasonably assumed to be unrelated to the unobserved values conditional on the observed data. Therefore, for the purpose of statistical analysis, it is reasonable to assume that these missing data are missing at random (MAR) and the statistical models that require MAR assumption are appropriate. In some cases, sensitivity analyses may be performed to assess the impact of missing data and the robustness of the conclusion.

8.3 Primary Efficacy Endpoint and Analyses

8.3.1 Primary Efficacy Endpoint

The primary endpoint is the National Institutes of Health Stroke Scale (NIHSS) total score during the Treatment Period.

8.3.2 Handling of Missing Data for the Primary Efficacy Endpoint

Missing data will not be imputed for the primary analysis, which will be based on an MMRM model.

8.3.3 Primary Efficacy Analysis

The primary efficacy analysis will be based on the monthly-adjusted area under the curve (AUC) derived from an MMRM. The dependent variable is the NIHSS total score during the Treatment Period. The model will include the stratification factors of tPA use (Y/N), EVT use (Y/N), time since last known normal (≤ 12 hours, > 12 hours based on time between last known normal and study drug initiation), main effects of treatment group and visit, and the treatment-by-visit interaction. The REPEATED statement will be used for visit with blocks in the covariance matrix identified by subject nested within treatment group. The unstructured covariance structure will be used to estimate the within subject variance-covariance; if the model does not converge with this variance-covariance structure, then compound symmetry will be used.

The monthly-adjusted AUC of NIHSS total score for each treatment group will be obtained using the trapezoidal method where i = treatment group (placebo, elezanumab) and j = visit during the Treatment Period {Day 1, Day 2-4, Week 4, Week 8, Week 12, Week 24, Week 36, Week 52}:

$$AUC_i = \frac{1}{13} \sum_{j=Stabil.(Day 2-4)}^{Week 52} \frac{(Week Number_j - Week Number_{j-1})}{4} \frac{1}{2} (LS Mean_{i,j} + LS Mean_{i,j-1})$$

The AUC for each treatment group, as well as the difference in AUCs (placebo minus elezanumab) and their respective standard errors and confidence intervals will be presented.

The posterior probability that the difference in AUCs being greater than 0.6 based on the observed data will be presented.

The attributes of the estimand corresponding to the primary efficacy objective are summarized in [Table 1](#).

Table 1. Summary of the Estimand Attributes Corresponding to the Primary Efficacy Objective

Estimand Label	Attributes of the Estimand					Statistical Summary
	Treatment	Endpoint	Population	Handling of Intercurrent Events		
NIHSS total score AUC	Elezanumab 1800 mg or placebo IV Q4W (13 doses)	NIHSS total score at each visit	FAS	Missing data due to intercurrent events (e.g., premature discontinuation of study drug, lost to follow-up, death, COVID-19) will be handled using MMRM with MAR assumption	Difference in monthly-adjusted AUC between treatment groups	

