- ✓ 7. NIHSS total score of 7 to 21, inclusive. NIHSS eligibility must be confirmed within 1 hour before randomization. For subjects treated with IV tPA \pm EVT, NIHSS must be confirmed \geq 1 hour after completion of all treatments and once any confounding effects of sedation or anesthesia have resolved.
- ✓ 8. No evidence of acute seizure at the onset of index stroke based on assessments conducted per standard of care. Subjects with evidence of seizure at onset of index stroke, but with imaging conclusively demonstrating an acute ischemic stroke are still allowed.
- ✓ 9. No evidence of acute myocardial infarction based on assessments per standard of care (e.g., elevated troponin levels, abnormal ECG).
- ✓ 10. In the judgment of the investigator, symptoms are not considered likely to resolve within the subsequent few hours (e.g., transient ischemic attack [TIA]).

Subject History

- ✓ 11. Subjects or their legally authorized representative confirms that before index stroke, there was no substantial impairment in subject's ability to perform activities of daily living (e.g., dressing, eating, walking, bathing, toileting) without assistance, as defined by a modified Rankin Score (mRS) of 0 to 2 before the index stroke.
- ✓ 12. Subjects with a history of previous stroke more than 3 months before enrollment are allowed if they are no longer experiencing ongoing functional recovery and mRS remains 0 to 2 prior to index stroke.
- ✓ 13. No known history before randomization of clinically significant medical conditions (other than current acute ischemic stroke) or any other reason, including any physical, psychological, or psychiatric condition that in the investigator's opinion would compromise the safety or interfere with the subject's participation in this study, or would make the subject an unsuitable candidate to receive study drug, or would put the subject at risk by participating in the study. Subjects with comorbid conditions that are, in the opinion of the investigator, clinically stable and not expected to meaningfully progress in the following 12 months may be considered eligible.
- ✓ 14. No known medical history of repeated episodes of complex migraine (e.g., weakness, vision, difficulty speaking). Subjects with history of complex migraine, but with imaging conclusively demonstrating an acute ischemic stroke are still allowed.

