7.3 Statistical Analyses for Efficacy

General Considerations

Analysis of the primary, secondary, and all other efficacy endpoints will be conducted on the FAS based on treatment as randomized, unless otherwise specified in the SAP.

The primary and secondary endpoints will be assessed using Bayesian methodology. No formal hypothesis tests will be performed. Additional efficacy endpoints will be summarized using descriptive statistics including the number of observations, mean, standard deviation, minimum, median, and maximum for continuous variables, and number and percent for categorical variables.

For continuous exploratory efficacy endpoints, the between-group treatment summary at each visit will be conducted using a mixed effects model with repeated measures (MMRM) including treatment group, visit, treatment-by-visit interaction, and stratification factors as fixed effects, the baseline values associated with the endpoint as covariates unless otherwise noted in the SAP. Missing data will not be imputed before performing the MMRM.

For binary efficacy endpoints, the frequency and percentage will be provided by treatment group. Missing values will be imputed as non-responders unless otherwise specified in the SAP.

Primary Efficacy Analysis

The primary analysis on NIHSS total score during the Treatment Period will be based on the AUC derived from an MMRM. The monthly-adjusted AUC of NIHSS total score for each treatment group will be obtained using the trapezoidal method and will be adjusted for month by dividing by 12. The MMRM model will include covariates of time since last known normal (≤ 12 hours, > 12 hours based on actual time of study drug initiation), IV tPA use, EVT use, main effects of treatment group and visit, and treatment-by-visit interaction. Each visit by a subject will serve as a repeated measure.

The posterior probability of the treatment group difference (with treatment showing greater improvement than placebo) in monthly-adjusted AUCs being greater than 0.6 using a noninformative prior will be calculated.

Secondary Efficacy Analysis

The secondary efficacy analysis is the proportion of subjects with a favorable outcome based on an mRS at Week 52 of 0, 1, or 2. The posterior probability of the treatment group difference (with treatment showing greater improvement than placebo) in responder rates being greater than 6.25% will be calculated using a non-informative prior.

Additional Efficacy Analyses

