7.2 Medical History

Medical history data will be coded using the Medical Dictionary for Regulatory Activities (MedDRA). The actual version of the MedDRA coding dictionary will be noted in the statistical tables and clinical study report. The number and percentage of subjects in each medical history category (by MedDRA system organ class (SOC) and preferred term) will be summarized overall and by treatment group for the FAS. The SOC will be presented in alphabetical order, and the preferred terms will be presented in alphabetical order within each SOC. Subjects reporting more than one condition/diagnosis will be counted only once in each row (SOC or preferred term).

The following stratification factors related to the current stroke will be summarized with the number and percentage of subjects in each category:

- Time since last known normal (\leq 12 hours between last known normal and study drug initiation, $>$ 12 hours between last known normal and study drug initiation) based on the stroke history eCRF. Randomization is stratified by time from last known normal to randomization transaction (\leq 11 hours or $>$ 11 hours) for operational purposes. Time from last known normal to study drug initiation will be used for analysis purposes.
- Treatment with tPA (Yes, No) based on the prior and concomitant medications and supplements eCRF.
- Treatment with EVT (Yes, No) based on the prior and concomitant procedures eCRF.
- Treatment with EVT and/or tPA (Yes, No) based on the eCRFs noted above. Yes indicates treatment with either or both EVT and tPA, and No indicates treatment with neither.

Additionally, the number and percentage of subjects with baseline NIHSS total score categories of $<$ 15, and \geq 15, and the number and percentage of subjects with reperfusion as measured by the modified Thrombolysis in Cerebral Infarction (mTICI)² score ($<$ 2B, \geq 2B) as reported by the central reader will be summarized by treatment group. Baseline NIHSS total score will also be summarized continuously.

Time between last known normal and study drug initiation will be summarized both as a continuous variable and a categorical variable (0 - 6 hours, $>$ 6 - 12 hours, $>$ 12 - 18 hours, $>$ 18 - 24 hours, $>$ 24 hours).

Discharge destination, time from last known normal to discharge post-stroke in days, and stroke subtype based on the Stroke History eCRF will be summarized.

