8.0 Efficacy Analyses

8.1 General Considerations

All efficacy analyses will be conducted in the FAS. Where noted, some analyses may additionally be conducted in the MMIAS. Because this is a small, exploratory, proof of concept study, p-values will not be presented. Where statistical models are noted, appropriate point estimates and 95% confidence intervals will be presented.

The primary analysis of efficacy endpoints will be performed after all ongoing subjects have completed the Treatment Period and an interim lock has been performed. This will be the final analysis for the efficacy endpoints during the Treatment Period.

Post treatment efficacy analyses will be completed following the final database lock.

Generally, "Baseline" refers to the last non-missing observation before the first administration of study drug. Where noted, Day 2-4 or Week 4 may be used as baseline. Unless otherwise specified, categorical variables will be summarized with the number and percentage of subjects in each category. Responder analyses will be presented with the number and percentage of subjects in each category, the difference in proportion of responders between the 2 treatment groups, and the 95% confidence interval for the difference based on Wald confidence limits, unless otherwise specified. Continuous variables will be analyzed using Mixed-Effect Model for Repeat Measures (MMRM) method. The dependent variable will be the visit value and baseline (pre-dose, Day 2-4 or Week 4, depending on the endpoint) will be included as one of the timepoints in the repeated measures. For analyses of change from baseline (pre-dose, Day 2-4 or Week 4, depending on the endpoint), this will be derived from a contrast of the group-level least squares (LS) means from the MMRM.

Unless otherwise specified, any subject who is randomized based on a wrong stratum will be analyzed according to the actual stratum the subject belongs to based on the eCRFs as noted in Section [7.2](#).

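### The primary NIHSS AUC difference is not adjusted for baseline NIHSS, so precision is lost and the result moves with chance baseline imbalance

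*SAP*

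**What the plan says.** SAP 8.3.3 gives the primary model in full: "The model will include the stratification factors of tPA use (Y/N), EVT use (Y/N), time since last known normal", then treatment group, visit and treatment-by-visit. Protocol 7.3 has the same list ("The MMRM model will include covariates of time since last known normal", with tPA, EVT, treatment, visit and the interaction). Neither names baseline NIHSS.

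The AUC formula in SAP 8.3.3 counts Day 1 among its visits. SAP 8.1 states the general rule that "baseline (pre-dose, Day 2-4 or Week 4, depending on the endpoint) will be included as one of the timepoints in the repeated measures". SAP 8.2 describes a default MMRM that instead has "the continuous fixed covariates of baseline measurement, unless otherwise noted".

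Practice differs elsewhere in the plan. The GLMM in SAP 8.2 "will include baseline NIHSS as a covariate", and so does the NIHSS subgroup ANCOVA in SAP 8.6. Protocol 7.3 adjusts the exploratory continuous endpoints for their baseline values. The secondary GLMM in SAP 8.4 does not adjust for NIHSS.

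On covariance, SAP 8.3.3 starts from an unstructured matrix, and "if the model does not converge with this variance-covariance structure, then compound symmetry will be used".

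The baseline score is available. Criterion 7 in Protocol 5.1 requires a score of 7 to 21, and "NIHSS eligibility must be confirmed within 1 hour before randomization". SAP 7.2 will tabulate it: "Baseline NIHSS total score will also be summarized continuously". It is not among the stratification factors in SAP 2.3.

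**The concern.** With a treatment-by-visit interaction and no constraint on Day 1, each arm has its own Day 1 mean. With complete data, the arm differences at later visits are then raw differences apart from the three stratification terms. Having Day 1 as a response helps only to recover missing later values under MAR. It does not correct for one arm starting worse.

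The AUC is a level, not a change. If patients who start worse tend to stay worse, a chance Day 1 difference passes into the quantity compared with 0.6. The main readout is a single posterior probability from about 120 patients. A reader who sees an imbalance in the baseline table will have no adjusted AUC to turn to in the visible plan, and adjustment chosen at that stage would not be credible.

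**Working it through.** **What cannot be reproduced.** The true difference, target probability, mortality and dropout behind the sample size are redacted (Protocol 7.7, SAP 2.4), and no SD is shown. The size of the problem therefore rests on assumptions.

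**Inputs from the documents.** About 120 patients 1:1, so n = 60 per arm; threshold 0.6; the eight visits and divisor 13 of SAP 8.3.3.

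**Assumptions.** Baseline SD 4 (a uniform spread over 7 to 21 would give 4.3); later SD 6; correlation between later visits 0.95 per visit step; Day 1-to-later correlation r = 0.3, 0.5 or 0.7 after tPA, EVT and time, either constant or multiplied by 0.95 per step from Day 1; Day 2-4 placed at day 3.

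**Step 1, weights.** The trapezoid rule gives w = 0.004, 0.038, 0.073, 0.077, 0.154, 0.231, 0.269, 0.154 for Day 1 to Week 52. Day 1 itself hardly counts. The effect comes through its correlation with later visits.

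**Step 2, formulas.** Let S be the within-patient covariance matrix, S0 its Day 1 column and S00 the Day 1 variance.
- Unadjusted variance of the AUC difference: (2/n) w'Sw.
- Adjusted variance: (2/n)[w'Sw − (w'S0)²/S00].
- Shift in the AUC difference per point of Day 1 difference: w'S0/S00.

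**Step 3, worked case (r = 0.5, constant).** w'Sw = 32.8, so the unadjusted SE is √(32.8/30) = 1.05. w'S0 = 0.004 × 16 + 0.996 × (0.5 × 4 × 6) = 12.0. Adjusted: 32.8 − 12.0²/16 = 23.8, so the SE is √(23.8/30) = 0.89, a 28% cut in variance. The Day 1 difference has SE 4√(2/60) = 0.73. One SE of imbalance shifts the AUC difference by (12.0/16) × 0.73 = 0.55.

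| r | Pattern | Adjusted SE (unadjusted 1.05) | Variance cut | Shift per 1-SE imbalance |
|---|---|---|---|---|
| 0.3 | constant | 0.99 | 10% | 0.33 |
| 0.5 | constant | 0.89 | 28% | 0.55 |
| 0.7 | constant | 0.71 | 54% | 0.77 |
| 0.3 | decaying | 1.01 | 6% | 0.26 |
| 0.5 | decaying | 0.95 | 17% | 0.43 |
| 0.7 | decaying | 0.86 | 33% | 0.60 |

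Simulation with an estimated covariance and three binary covariates (4,000 trials per case) gave cuts of 9%, 26% and 54% (constant) and 6%, 17% and 32% (decaying). With 20% and 40% dropout at r = 0.5 the cuts were 26% and 25% (constant), 16% and 15% (decaying). If both the later-visit correlation and the baseline decay are 0.85 per step, the cut is only 3% to 14%. With step correlation 0.85 but decay 0.95 it is 7% to 39%.

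**Step 4, effect on the readout.** Under a flat prior, the chance that P(difference > 0.6) exceeds 80% is 1 − Φ((0.6 + 0.842 SE − d)/SE). The 80% cut-off and d = 1.5 are assumptions. At r = 0.5, adjustment moves this from 7.8% to 6.5–7.1% when d = 0, and from 51% to 54–57% when d = 1.5.

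Within one trial the movement is larger. Take an AUC SD of 5, baseline-to-AUC correlation 0.5 and a balanced-arm estimate of 1.2. The SE is 5√(2/60) = 0.91 and the shift per point is 0.5 × 5/4 = 0.62. P(difference > 0.6) is 0.74 with balanced arms, 0.91 if placebo starts 1 point worse, and 0.49 if elezanumab does. A difference of at least 1 point arises in 17% of trials at baseline SD 4 (12% to 21% for SDs of 3.5 to 4.3).

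**Step 5, cost of adjusting.** Estimating the slope costs about 1/115 = 0.9% of variance with complete data. Adjustment loses only if Day 1 NIHSS correlates with the AUC below √0.009 ≈ 0.09.

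**Step 6, compound-symmetry fallback.** S is replaced by a matrix with its average variance and average covariance, and the model SE is set against the true SE (complete data).

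| Model | Model SE | True SE | Ratio | Null chance of posterior > 80% |
|---|---|---|---|---|
| Current | 0.94–0.98 | 1.05 | 0.90–0.94 | 8.7–9.1% |
| Baseline as covariate | 0.70–1.00 | 0.71–1.01 | 0.96–0.99 | 4.8–7.7% |
| Common Day 1 mean | 0.44–0.51 | 0.73–1.05 | 0.48–0.60 | 9.2–16.4% |

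**The case against.** The strongest reply is that nothing here is invalid. The model is pre-specified, unbiased and has a valid standard error, in a study with no formal hypothesis tests and no type I error control. That stands: this is a matter of efficiency and of robustness to imbalance, not of error. It does not remove the case for an adjustment that uses data already collected.

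It can be said that the default in SAP 8.2 already brings baseline in. It yields where another section notes otherwise. SAP 8.3.3 gives its own list and counts Day 1 as a visit, so the natural reading is that baseline is a response. The SAP should still say so.

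SAP 8.3.4 reports change from Day 1 at each visit, and Protocol 7.3 plans subgroups by baseline NIHSS. These would expose an imbalance but do not adjust the AUC. Nor is subtraction a substitute: a baseline-subtracted AUC cuts variance by 24% (constant) or 9% (decaying) at r = 0.5, but raises it by 5% to 14% at r = 0.3. Parts of SAP section 8 are blacked out, so the absence of an adjusted AUC can be asserted only for the visible text.

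The size is assumed and could be small. With a later SD of 4 and constant r, the one-SE shift would be 0.22 to 0.51. The direction does not depend on these choices, only the amount.

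**Conclusion.** The concern holds. As written, the AUC difference compared with 0.6 is unadjusted for baseline NIHSS. Under the stated assumptions the variance is higher than it need be by an amount that adjustment would cut by 6% to 54%, or as little as 3% if correlations fade quickly. A one-SE imbalance moves the contrast by 0.26 to 0.77 points. The average gain in the chance of a high posterior is a few percentage points. The larger benefit is that the trial's single result no longer depends on which arm happened to start worse. Confidence is high that the term is missing and that adding it helps, and lower on how much. It should be fixed, but it does not invalidate the analysis.

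**What to change.** In SAP 8.3.3 and Protocol 7.3, remove Day 1 from the responses, add baseline NIHSS and baseline-by-visit as covariates, and use the common baseline mean for Day 1 in both arms' AUC. This form stays close to calibrated if compound symmetry has to be used.

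A model with Day 1 as a response and a common mean is an alternative only if the compound-symmetry fallback is replaced or paired with robust (sandwich) standard errors. Under compound symmetry its model SE is about 40% to 50% too small. Heterogeneous AR(1) or Toeplitz structures do not fully repair this (ratios 0.62–0.81 and 0.75–0.80), whereas robust standard errors brought the null chance back to 4.8–7.8%.

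State in SAP 8.1 and 8.2 which form governs the primary MMRM. Keep the current AUC as a supportive analysis. The change-from-baseline contrasts in SAP 8.3.4 then come from that retained model or use the common baseline mean. Report how many FAS patients have no NIHSS after Day 1, since they leave the adjusted model.

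The cost is wording in both documents, ethics committee approval of the protocol amendment (Protocol 8.1), one changed model statement and about 0.9% of variance. It needs no new data or patients. Make the change before the randomization is loaded at the interim lock (SAP 2.3).
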